1.1 How will you define adverse events (AE)) for this study?

Page 13 of 24 Version Date: 2-29-12

Assessment of the sensitivity of the hypothalamic GnRH pulse generator to estradiol and progesterone inhibition in early pubertal girls (JCM026)

An adverse event will be considered any undesirable sign, symptom or medical or psychological condition **even if the event is not considered to be related** to the investigational drug/device/intervention. Medical condition/diseases present before starting the investigational drug/intervention will be considered adverse events only if they worsen after starting study treatment/intervention. An adverse event is also any undesirable and unintended effect of research occurring in human subjects as a result of the collection of identifiable private information under the research. Adverse events also include any problems associated with the use of an investigational device that adversely affects the rights, safety or welfare of subjects.

Will use definitions provided in the non IRB Protocol (Sponsor's, Investigator-Initiated, CTEP etc.) located in Section (insert section #).

Other

1.2 How will you define serious adverse events?

A serious adverse event will be considered any undesirable sign, symptom, or medical condition which is fatal, is life-threatening, requires or prolongs inpatient hospitalization, results in persistent or significant disability/incapacity, constitutes a congenital anomaly or birth defect, is medically significant and which the investigator regards as serious based on appropriate medical judgment. An important medical event is any AE that may not result in death, be life-threatening, or require hospitalization but may be considered an SAE when, based upon appropriate medical judgment, it may jeopardize the patient and may require medical or surgical intervention to prevent one of the outcomes listed in the definitions of SAEs.

OR

Any serious psychological and emotional distress resulting from study participation (suggesting need for professional counseling or intervention).

1.3 This is the definition of an **unanticipated problem**:

- An unanticipated problem is any event, experience that meets ALL 3 criteria below:
 - Is unexpected in terms of nature, severity or frequency given the research procedures that are described in the protocol-related documents AND in the characteristics of the subject population being studies
 - Related or possibly related to participation in research. This means that there is a reasonable possibility that the incident may have been caused by the procedures involved in the research study.
 - The incident suggests that the research placed the subject or others at greater risk of harm than was previously known or recognized OR results in actual harm to the subject or others

1.4 This is the definition of **a protocol violation**:

A protocol violation is defined as any change, deviation, or departure from the study design or procedures of research project that is NOT approved by the IRB-HSR prior to its initiation or

Assessment of the sensitivity of the hypothalamic GnRH pulse generator to estradiol and progesterone inhibition in early pubertal girls (JCM026)

implementation, OR deviation from standard operating procedures, Good Clinical Practices (GCPs), federal, state or local regulations. Protocol violations may or may not be under the control of the study team or UVa staff. These protocol violations may be major or minor violations.

Major Protocol Violation:

All major protocol violations must be reported to the IRB-HSR immediately upon discovering them, and no later than seven (7) calendar days from the time the study team receives knowledge of the event. A major violation is a protocol violation that meets the following criteria:

- Represent a serious or continuing failure on the part of the study team to comply with the protocol, standard operating procedures, GCPS, federal, state or local regulations
- Impacts subject safety or substantially alter risks to subjects. May or may NOT result in actual harm (clinical, emotional, social, financial, etc)
- Significantly damages the completeness, accuracy and reliability of the data collected for the study
- Is under control of the investigator/study team/ UVa staff

Examples of **MAJOR** violations may include, but are not limited to:

- Evidence of willful or knowing misconduct on the part of the investigator(s), or study team
- Failure to obtain informed consent, i.e., there is no documentation of informed consent, or informed consent is obtained after initiation of study procedures. (Note: Data for subjects where consent is not documented may not be used in data analysis.)
- Enrollment of a subject who did not meet all inclusion/exclusion criteria which would affect subject safety or would negatively impact data integrity
- Performing study procedure not approved by the IRB-HSR
- Failure to report serious unanticipated problems/adverse events to the IRB-HSR and (if applicable), the sponsor
- Failure to perform study procedures outlined in the protocol where subject safety or data integrity may be negatively impacted. (Ex. Safety labs not done per protocol)
- Drug/study medication dispensing or dosing error under control of Investigators, study team or UVa staff.
- Study visit or procedure conducted outside of required time frame that may negatively affect subject safety
- Failure to follow Data Safety Monitoring Plan

Minor Protocol Violations:

Reporting of minor violations to IRB is not required by IRB-HSR.

2. Identified risks and plans to minimize risk

2.1 What risks are **expected** due to the intervention in this protocol?

Expected: is identified in nature, severity or frequency in the study documentation (protocol, consent, Investigator Brochure, package insert etc) is considered an expected.

Risk associated with frequent blood sampling:

Expected Risks related to study participation-	Frequency		
volume of blood drawn	Please pick one frequency from each box below		
• Significant anemia related to frequent	Occurs frequently,		
blood sampling (hematocrit $< 30\%$)	Occurs infrequently		
	Occurs rarely		
	Frequency unknown, but likely to be very rare		
• Mild anemia (hematocrit < 36%)	Occurs frequently,		
related to frequent blood sampling	Occurs infrequently		

Assessment of the sensitivity of the hypothalamic GnRH pulse generator to estradiol and progesterone inhibition in early pubertal girls (JCM026)

Frequency unknown	Occurs rarely
-------------------	---------------

Risk associated with micronized progesterone suspension:

Expected Risks related to study participation-	Frequency		
micronized progesterone			
• GI upset (nausea, abdominal bloating,	Occurs frequently,		
diarrhea)	Occurs infrequently		
	Occurs rarely		
	Frequency unknown, but likely to be very rare		
• CNS effects (sleepiness, headache,	Occurs frequently,		
dizziness, fatigue, emotional lability,	Occurs infrequently		
irritability)	Occurs rarely		
•	Frequency unknown		
• Mild, short-lived vaginal bleeding	Occurs frequently,		
shortly after ingestion	Occurs infrequently		
	Occurs rarely		
	Frequency unknown		

Risk associated with estradiol:

Expected Risks related to study participation.	Frequency		
• GI upset (nausea, abdominal bloating, diarrhea)	 ☐ Occurs frequently, ☑ Occurs infrequently ☐ Occurs rarely ☐ Frequency unknown 		
Breast Tenderness	Occurs frequently, Occurs infrequently Occurs rarely Frequency unknown		
• Deep vein thrombosis	 Occurs frequently, Occurs infrequently Occurs rarely Frequency unknown, however occurs very rarely with long-term estrogen use (as with oral contraceptive pills), so would expect to be exceedingly rare with the short term administration in this protocol 		

Risk associated with IV needle placement:

Expected Risks related to study participation- IV placement	Frequency		
Infection at needle site	 Occurs frequently, Occurs infrequently Occurs rarely Frequency unknown, but likely to be very rare 		
• Bleeding at needle site	 ☐ Occurs frequently, ☐ Occurs infrequently ☑ Occurs rarely 		

Assessment of the sensitivity of the hypothalamic GnRH pulse generator to estradiol and progesterone inhibition in early pubertal girls (JCM026)

Frequency unknown
Occurs frequently,
Occurs infrequently
Occurs rarely
Frequency unknown
Occurs frequently,
Occurs infrequently
Occurs rarely
Frequency unknown
Occurs frequently,
Occurs infrequently
Occurs rarely
Frequency unknown

Risk associated with iron supplementation

Expected Risks related to study participation-	Frequency		
iron supplementation	Please pick one frequency from each box below		
• nausea	Occurs frequently,		
	Occurs infrequently		
	Occurs rarely		
	Frequency unknown		
constipation	Occurs frequently,		
-	Occurs infrequently		
	Occurs rarely		
	Frequency unknown		
dark or black stools	Occurs frequently,		
	Occurs infrequently		
	Occurs rarely		
	Frequency unknown		

Risk associated with EMLA cream (topical lidocaine and prilocaine, used to alleviate pain): The risks of lidocaine and prilocaine in general may include (frequency not defined) hypotension, angioedema, shock, hyperpigmentation, erythema, itching, rash, burning, urticaria, burning, stinging, edema bronchospasm, and hypersensitivity reactions. However, in the case of topical lidocaine/prilocaine use, the non-dermatologic adverse events mentioned above would be extremely unlikely unless large amounts of topical lidocaine/prilocaine were used (allowing significant systemic absorption).

Risk regarding wrist actigraphy: There are no known risks associated with the use of wrist actigraphy.

Risk of not being able to take hormonal medications: Fertility in premenarcheal girls is exceedingly unlikely. Thus, the risk of pregnancy related to inability to take hormonal birth control medication is virtually absent.

- 2.2 List by bullet format a summary of safety tests/procedures/observations to be performed.
 - Sterile technique will be used.
 - Before participation in the study, all participants will be required to have a normal hemoglobin (≥ 11.0 g/dl for African American subjects or ≥ 11.5 g/dL for non-African American subjects). Hemoglobin levels will be measured prior to every admission, and the admission will only continue if the

Assessment of the sensitivity of the hypothalamic GnRH pulse generator to estradiol and progesterone inhibition in early pubertal girls (JCM026)

hemoglobin level is ≥ 11.0 g/dl for African American subjects or ≥ 11.5 g/dL for non-African American subjects.

- Blood loss will be carefully recorded and limited to a maximum of 7cc/kg (10% of estimated total blood volume) in 8 weeks. A total of 216.5 ml of blood will be drawn during the study (including estimated waste from frequent blood draws). Therefore, girls weighing less than 31 kg will not be able to participate. Iron supplementation (325 mg once or twice a day dependent on weight) will be prescribed to all participants.
- β -hCG levels will be measured at screening and prior to each admission; if the β -hCG is positive, the study will be discontinued.
- Topical lidocaine and prilocaine (EMLA) cream may be used to lessen pain associated with IV needle insertion.
- 2.3 Check the criteria below under which an INDIVIDUAL SUBJECT'S study treatment or study participation would be stopped or modified

At subject, PI or sponsor's request

Treatment would be stopped if the subject had a Serious adverse event deemed related to study

The study would be stopped in the patient has a positive pregnancy test or a hematocrit <36 and hemoglobin <12 prior to any of the 4 admissions.

2.4 Check the criteria under which THE ENTIRE STUDY would need to be stopped. These are called stopping rules for early termination of the entire study.

⊠Per IRB, PI, DSMB, or sponsor discretion

 \bigcirc Other: If there are an excessive number of unexpected adverse events that significantly alter the risk/benefit ratio for the study, the study will be terminated. All adverse events will be evaluated both individually and cumulatively by the study team and principal investigator as they arise, allowing for timely decisions regarding study continuation/termination.

- 2.5 Describe the criteria for breaking the blind/mask 🖾 NA Not blinded/masked
- 2.6 How will subject withdrawals/dropouts be reported to the IRB prior to study completion?☑ IRB-HSR continuation status form

3. Adverse Event / Unanticipated Problem Recording and Reporting

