Criteria for inclusion:

- Girls ages 8 to 14
- Tanner 1-3 pubertal stage
- Pre-menarchal
- Normal screening labs

Criteria for exclusion:

- Abnormal screening labs
- congenital adrenal hyperplasia.
- Hyperandrogenism (e.g., hirsutism, elevated free testosterone level)
- Hemoglobin <11.5 g/dL for non-African American subjects; Hemoglobin < 11.0 g/dL for African American subjects
- Weight < 31 kg
- History of peanut allergy, deep venous thrombosis, breast cancer, endometrial cancer, or cervical cancer
- On hormonal medications (including oral contraceptive pills) or on medications known to affect the reproductive axis within 3 months of the study
- Pregnant or breast feeding
- Participation in a research study within the past 30 days that involved taking a study drug.
- Participation in a research study that involved taking up to or greater than 473 ml's of blood within the past 60 days.
- Cigarette smoking
- History of surgery that required bedrest within the past 30 days
- Family history of hypercoagulability or unexplained thromboembolic disease (not in setting of bedrest, surgery, or malignancy)

Assessment of the sensitivity of the hypothalamic GnRH pulse generator to estradiol and progesterone inhibition in early pubertal girls (JCM026)

• In order to ensure an adequate number of younger girls, no more than 4 enrolled subjects will be Tanner stage 3

Restrictions (if any) **on use of other drugs or treatments:**

Subjects must discontinue all hormonally-active medications at least 3 months prior to the frequent sampling study (and 2 months prior to screening visit) and must not take any other medications known to affect the reproductive axis during the study. There are no dietary requirements for this study.

Recruitment

How will participants be recruited?

- _X__ Posters/Flyers
- _X__ Television
- X Radio
- X Newspaper Ads
- X_____ Internet
 - Medical Record/ Database Review. NOTE- potential subjects will be contacted after obtaining the approval of their attending physician and IRB-HSR approval of method of contacting potential subjects (i.e. letter)
 - ____ Medical Record/ Database Review. NOTE- subjects will not be contacted
 - X___ Referrals from other health care professionals
- X Discuss protocol with patients of PI or sub-investigators during a standard clinical visit

If subjects will be contacted, explain in detail how this will be done.

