After a potential subject is identified, we will arrange for her to come to the CRU or alternate UVA clinical unit for an outpatient screening exam. The goals and procedures of the study will be explained to the potential subject and her parents, and they will be given the opportunity to ask any questions. The potential subject and her parents will be asked to sign the assent and consent forms. A physician will record a family and personal medical history and perform a physical exam. Subjects will need to fast for a minimum of 8 hours prior to screening blood draw. Blood will be drawn for screening tests (CBC, Comprehensive metabolic panel, prolactin, LH, FSH, E₁, E₂, P, total T, androstenedione, 17-OHP, DHEA-S, fasting insulin, glucose, TSH, hCG, cholesterol, LDL, HDL, and SHBG). Potential subjects must fall within the normal range on all blood tests to be admitted to the study. Patients with elevated 17-OHP on screening will be referred to their pediatricians for further testing to rule out congenital adrenal hyperplasia. They will only be able to continue with the study if the have documented normal 17-OHP levels following cotrosyn stimulation. If the subject's hemoglobin is low at the time of screening (< 11.0 g/dL for African American subcets or < 11.5 g/dL for non-African American subjects), we will offer the option of taking oral iron supplementation at a dose of 1-2 mg/kg for 60 days. Subjects weighing \leq 36 kg will be given 300-325 mg oral ferrous gluconate daily (containing 36 mg of elemental iron); subjects weighing \geq 36 kg will be given 300-325 mg oral ferrous gluconate twice daily.

Assessment of the sensitivity of the hypothalamic GnRH pulse generator to estradiol and progesterone inhibition in early pubertal girls (JCM026)

Following the course of iron supplementation, the subject will then return to the CRU or clinical unit for a repeat hemoglobin, and will only be able to proceed with the study if her hemoglobin is greater than or equal to 11.5 g/dL for non-African American subjects and greater than or equal to 11.0 g/dL for African American subjects.

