If the screening tests show that the subject is eligible for the study, she will be given oral iron supplementation at a dose of 1-2 mg/kg for 30 days to help prevent anemia during and after the study. Subjects weighing \leq 36 kg will be given 300-325 mg oral ferrous gluconate daily (containing 36 mg of elemental iron); subjects weighing >36 kg will be given 300-325 mg oral ferrous gluconate twice daily. The admission can take place any time during or after the iron supplementation.

If overnight admission is scheduled to occur greater than one month after the most recent hemoglobin (such as that obtained during screening), a hemoglobin will be repeated 2-5 days before the overnight admission. Documentation of hemoglobin ≥ 11.5 g/dL for non-African American subjects or ≥ 11.0 g/dL for African American subjects in the previous month is required for the frequent sampling protocol. If the overnight admission is scheduled to occur greater than 3 months after screening, then the safety labs (complete blood count, comprehensive metabolic panel) will be repeated at this time.

Day 0: First inpatient admission

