Assessment of the sensitivity of the hypothalamic GnRH pulse generator to estradiol and progesterone inhibition in early pubertal girls (JCM026)

0700, 1500, and 2300 hr to achieve mean plasma concentrations over the range of 2-8 ng/ml for seven days. Each subject will be instructed to eat a small snack with the medication. It has been observed that the absorption of progesterone is influenced by the presence or absence of food. Subjects will continue their iron supplementation.

Days 3, 5: Outpatient blood draws

On study day 3, subjects will have blood drawn at 0900 or 1700 hr (two hours after the 0700 or 1500 hr progesterone dose) to check serum estrogen and peak progesterone levels. On study day 5, subjects will have blood drawn at 0900 or 1700 hr (two hours after the 0700 or 1500 hr progesterone dose) to check serum estrogen, peak progesterone levels, and hematocrit/hemoglobin. For the second admission to continue, subject must have a hemoglobin ≥ 11.0 g/dL for African American subjects or ≥ 11.5 g/dL for non-African American subjects.

Day 7: Second inpatient admission

The second inpatient admission will begin on day 8. The procedure will be identical to the first inpatient admission.

Follow-up

Subjects will discontinue estrace, progesterone, and iron after the completion of the second inpatient admission. Follow-up questionnaires and/or phone interviews will be completed by the subjects 3, 6 and 12 months after the study asking about the onset and frequency of menses and changes in hirsutism. During these interviews, we will specifically address whether pre-menarchal girls had a withdrawal bleed following the study, and if so, whether or not they subsequently continued menstruating. Whenever possible we will also see the patients on 2-3 occasions during the 12 months to obtain blood for T, DHEA-S, E₂, and P measurements (depending on cycle stage).

If a potential subject does not meet the inclusion/ exclusion criteria will you repeat any of the screening procedures/ tests? Yes

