All participants will receive a \$75 Charlottesville Fashion Square Mall gift card per inpatient admission. In addition, participants will receive a \$50 bonus for study completion, also in the form of a gift card. Therefore, a participant who completes the entire study will receive a total of \$200 in gift cards. If a subject only completes one inpatient admission, she will be given a \$75 gift card.

Is money paid from UVa or State funds (including grant funds)? Yes

If Yes, continue to check all that apply below

Will research	ner use any o	f the following to	o compensate	participants	(check all	that apply)?
	2	U U	1	1 1		11 2/

____ Check issued to participant via UVA Oracle or State system

- _____ Petty cash account
- __X__ Gift card

Other type of compensation: specify :_____

Check **all** categories that apply based on each participant group in the study:

<\$50 TOTAL possible compensation for participating in the research study over one year

>= \$50 TOTAL possible compensation for participating in the research study over one year **and** check issued to participant via UVA Oracle or State system

____X___ >= \$50 TOTAL possible compensation for participating in the research study over one year **and** researcher unable to issue checks through UVA or State system, but able to gather IRS information **No payments of >= \$50 will be approved if IRS information cannot be obtained.**

Justify why you are unable to issue checks through the UVa Oracle or state system.

Additional Comments/ Explanation:

This study involves preadolescent and adolescent girls. In past and on-going studies involving the same patient population, we have found that the girls prefer being given gift cards directly at the end of the study to receiving

Page 11 of 24 Version Date: 2-29-12

Assessment of the sensitivity of the hypothalamic GnRH pulse generator to estradiol and progesterone inhibition in early pubertal girls (JCM026)

a check in the mail 4-6 weeks later, and this preference is reflected in our ability to recruit subjects. Therefore, we prefer to compensate these subjects with gift cards. We obtain social security numbers for IRS purposes.

Specimens:

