Type of specimen to be used: Blood Please list the information and identifiers that will be with the specimen when it is given to you. Name, medical record #, GCRC protocol #, time (date and clock hour) drawn. If you are using discarded tissue do you confirm that it will be obtained either from pathology, a clinical lab or the UVa Tissue Procurement Facility? Not applicable. Will you be using viable embryos? No Will you be using embryonic stem cells? No Do you plan to ship any specimens outside of UVA? No Will the specimen be obtained before a subject has signed a consent form? No

Study Design: Biomedical

What kind of controls will be used? Only normal control subjects will be studied.Single-blind, double-blind, other: This study is not blinded.If randomized, how? This study is not randomized.Does the study involve a placebo? No

Bio-statistical Analysis

Explain bio-statistical analysis to be done:

Sample Size Determination. If a total of 10 normal tanner-stage 1-3 girls complete both CRU admissions, and the true group to group difference in the percentage change in LH pulse frequency following estradiol and progesterone supplementation is greater than or equal to 30%, we anticipate that we will have at least an 80% chance of rejecting the null hypothesis that estradiol and progesterone supplementation alters LH pulse frequency to the same degree in both normal tanner-stage 1-3 and normal tanner-stage 4-5 girls. This effect size was determine based on the following set of assumptions: (a) the percentage change in LH pulses frequency following estradiol and progesterone supplementation is normally distributed in both study populations, (b) the within-subject measurement variability (standard deviation) in the percentage change LH pulse frequency will not exceed 26.6% in either group (standard deviation based on the data from IRB-HSR# 8588), (c) the two-sided type I error rate of the statistical test will not exceed 0.05, and (d) the power of the statistical test will be at least 0.80.

Base on our previous protocol (IRB-HSR# 8588), we anticipated that the subject dropout rate will not exceed 35% in this study population. Therefore, we intend to enroll 16 normal tanner-stage 1-3 girls into this study.

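### The individual stopping rule in section 2.3 uses a different anemia limit from the rest of the protocol and counts four admissions where the study has two

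*Combined protocol and SAP*

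**What the plan says.** Section 2.3 of the Data and Safety Monitoring Plan gives the criteria for stopping an individual girl. Besides a positive pregnancy test, it names "a hematocrit <36 and hemoglobin <12 prior to any of the 4 admissions". The two blood limits are joined by *and*, and one pair applies to all girls.

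Five other places set a limit on hemoglobin alone, split by race:

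- Criteria for exclusion: "Hemoglobin <11.5 g/dL for non-African American subjects; Hemoglobin < 11.0 g/dL for African American subjects".
- Outpatient Screening, repeat after iron: a girl "will only be able to proceed with the study if her hemoglobin is greater than or equal to 11.5 g/dL" if non-African American, with 11.0 g/dL for African American girls.
- Outpatient Screening, before frequent sampling: "Documentation of hemoglobin ≥ 11.5 g/dL for non-African American subjects or ≥ 11.0 g/dL for African American subjects in the previous month" is required.
- Days 3, 5: Outpatient blood draws: "For the second admission to continue, subject must have a hemoglobin ≥ 11.0 g/dL for African American subjects", with 11.5 g/dL for the others.
- Data and Safety Monitoring Plan, section 2.2: "Hemoglobin levels will be measured prior to every admission, and the admission will only continue if the" same 11.0/11.5 g/dL limit is met.

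Hematocrit is measured on day 5, but the condition to continue names hemoglobin only.

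On the number of admissions, the schedule has a first admission on day 0, a second about a week later, and no other. The sample size is conditioned on two: "If a total of 10 normal tanner-stage 1-3 girls complete both CRU admissions". Under Payment, "a participant who completes the entire study will receive a total of" $200, made up of $75 per admission and a $50 completion bonus.

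**The concern.** Sections 2.2 and 2.3 stand next to each other in the same safety plan, act at the same moment (before an admission) and can give different answers for the same girl. Staff looking at a day 5 result cannot tell from the protocol whether she continues.

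Three things are at stake.

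- **Safety.** This is the anemia limit for frequent blood sampling in healthy girls aged 8 to 14. For the lightest eligible girl the planned draw is close to the protocol's own ceiling: 216.5 mL / 31 kg = 6.98 cc/kg, against 7 cc/kg.
- **Compliance.** Section 1.4 lists failure to follow the safety plan among its examples of major violations. Admitting a girl who meets section 2.2 but is caught by section 2.3 could be classed that way.
- **Data.** The response variable is the change between the two admissions. A girl stopped before the second has no change score.

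**Working it through.** **1. Number of admissions.** With k admissions the payment is 75k + 50. Setting this equal to the stated $200 gives k = 2. Four admissions would pay 75 × 4 + 50 = $350.

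Blood volume agrees. Sampling every 10 minutes from 1900 to 0600 gives 11 × 6 + 1 = 67 samples of 0.75 mL. To these come the 2.5 mL samples every two hours and one 3.0 mL sample. The text leaves open whether the 2.5 mL samples replace or add to the small ones, and whether one is drawn at 0700, so a range is shown:

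- Low: 61 × 0.75 + 6 × 2.5 + 3.0 = 63.75 mL per admission
- High: 67 × 0.75 + 7 × 2.5 + 3.0 = 70.75 mL per admission

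Two admissions need 127.5 to 141.5 mL, inside the stated study total of 216.5 mL. Four would need 255 to 283 mL, above it, before screening, outpatient draws and waste.

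**2. The two rules applied to the same girls.** The value pairs are illustrative assumptions.

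| Group | Hemoglobin (g/dL) | Hematocrit | Section 2.3 | 11.5/11.0 limit |
|---|---|---|---|---|
| Non-African American | 11.7 | 35 | stop | continue |
| African American | 11.2 | 35 | stop | continue |
| Non-African American | 11.2 | 36.5 | no stop | barred |
| African American | 10.8 | 36.5 | no stop | barred |

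The first two rows are direction (1): cleared by the race-specific limit, stopped by section 2.3. The last two are direction (2): barred by the race-specific limit, not caught by section 2.3.

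**3. Width of the direction (1) band.** When hematocrit is below 36, the band is 12 − 11.5 = 0.5 g/dL for non-African American girls and 12 − 11.0 = 1.0 g/dL for African American girls.

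**4. How much of the band section 2.3 catches.** This depends on the ratio r of hematocrit to hemoglobin, which the documents do not give. Taking hematocrit = r × hemoglobin as an assumption, section 2.3 stops a girl when hemoglobin is below the smaller of 12 and 36/r.

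| r | Section 2.3 stops below | Non-African American band (11.5 to <12) | African American band (11.0 to <12) |
|---|---|---|---|
| 36/12 = 3.00 | 12.0 | all stopped | all stopped |
| 36/11.5 = 3.13 | 11.5 | none stopped | lower half stopped |
| 36/11.0 = 3.27 | 11.0 | none stopped | none stopped |

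At r = 3.00, the ratio of section 2.3's own pair, hematocrit is 11.5 × 3 = 34.5 and 11.0 × 3 = 33.0 at the two limits. Both are below 36, so the race-specific limits would never decide an admission. Direction (2) opens only above r = 3.13 (non-African American) or 3.27 (African American). No single ratio makes section 2.3 agree with both limits.

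**5. Room for lost pairs.** At the planned 35% dropout, 16 × 0.65 = 10.4 completers are expected against the 10 required. One further loss would leave 9.4. The protocol does not say whether the 35% already includes girls stopped for low hemoglobin.

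**The case against.** The strongest reply is that nothing here is strictly contradictory. The 11.5/11.0 g/dL limits are necessary conditions for going ahead, and section 2.3 adds a further reason to stop. Every rule can be obeyed together, the race-specific floor always binds, and no girl loses protection. In direction (2), section 2.3 fails to stop the girl, but section 2.2 and, before the second admission, the day 5 condition still bar her. On this view the worst outcome is some unnecessary stopping.

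Much of that is right. Direction (2) permits nothing that the other places forbid, so direction (1) carries the point. But the reply does not settle direction (1). If section 2.3 simply adds to the others, it replaces the limit that section 2.2 and day 5 state for the same admission, and the protocol nowhere says that this is intended.

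Other objections stand in part:

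- The exclusion criterion and the repeat after iron are entry limits, and an entry limit may differ from a stopping limit by design. The same-moment conflict is with the pre-sampling requirement, day 5 and section 2.2.
- The protocol's examples of major violations are things that may qualify, subject to listed criteria. The compliance risk is a possibility only.
- The ratio table rests on an exact proportionality and says nothing about how many girls are affected.
- The wrong admission count would mislead few readers, since the schedule is clear. Taken alone it is editorial.

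**Conclusion.** The concern holds: section 2.3 is wrong as written. It sets a limit that differs from the one stated in five other places, in value, in the added hematocrit condition and in having no race split. It also counts four admissions in a two-admission study.

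The conflict that matters is a band of 0.5 g/dL (non-African American) or 1.0 g/dL (African American) with hematocrit below 36, in which the plan both clears and stops the same girl. Depending on the assumed ratio, section 2.3 catches anything from all of that band (3.00) to none of it (3.27). How many of the up to 16 girls would be affected cannot be computed.

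The band widths and the admission count come straight from the protocol's figures. Only the share of the band caught, and the illustrative pairs, rest on assumption. Because this is a stopping rule for blood sampling in children, it should be settled before it is applied. Nothing here implies that either limit is the right one.

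**What to change.** Reconcile section 2.3 with section 2.2, the day 5 condition, the pre-sampling requirement, the repeat after iron and the exclusion criterion, so that the protocol gives one answer for any girl at entry, at each admission and for stopping. The investigators and the IRB should decide the rule. If they intend entry and stopping limits to differ, or section 2.3 to add to the others, the protocol should say so and state which governs. Change the count of four admissions to two.

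The cost is a wording amendment to one sentence, or to the places it is reconciled with. There is one dependency. The repeat test before an admission more than a month after the last hemoglobin names hemoglobin only, and the complete blood count is repeated only after three months. If a hematocrit condition is kept, that repeat would have to report hematocrit as well. No change to the statistical analysis is needed.
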